### **4. STUDY OBJECTIVES**

#### **4.1 Primary Objective**

- To determine the relative bioavailability of subcutaneous (SC) tirzepatide 5-mg injection into the thigh and upper arm compared to the abdomen.

#### **4.2 Secondary Objectives**

- To determine the relative bioavailability of SC tirzepatide 5-mg injection in subjects with different body mass indices (BMIs).
- To evaluate the safety and tolerability of SC tirzepatide 5-mg injection.

#### **4.3 Exploratory Objective**

- To explore the relationship between adiposity at injection site with tirzepatide exposure.

## 5. STUDY DESIGN

This is a single-center, open-label, 3-period, 3-sequence, randomized, crossover study conducted in overtly healthy male and female subjects in 2 BMI groups (low and high). The BMI groups will be as follows:

- Low BMI: 18.5 to 27.0 kg/m^2
- High BMI: 27.1 to 45.0 kg/m^2 – every effort will be made to enroll subjects so that approximately half of this group have a BMI above 35.0 kg/m^2

Subjects will be admitted to the clinical research unit (CRU) on Day -1 and will receive a single SC injection of tirzepatide 5 mg into 1 of 3 injection sites on Day 1, of each of the 3 treatment periods, with injection site sequence determined by the randomization.

[figure not shown]
The injection sites are:

- upper arm (Test 1)
- thigh (Test 2)
- abdomen (Reference)

Subjects will remain in the CRU until the scheduled assessments have been completed on Day 8. Subjects may be required to remain inpatient for a longer period if deemed necessary by the investigator for safety monitoring reasons. Subjects will attend 3 outpatient visits on Days 15, 21, and 36 of each treatment period for safety monitoring and PK sampling. The Day 36 visit of Treatment Period 3 will be considered the final follow-up visit.

There will be a washout period of at least 35 days between tirzepatide injections.

[Figure GPHI.1](#) illustrates the study design. This tirzepatide injection sequence shown is an illustrative example only. Each subject enrolled will be assigned a treatment sequence according to the actual randomization schedule provided to the site.

**Figure GPHI.1. Illustration of Study Design**

## 6. TREATMENTS

The TFLs will include a subheader for treatment (5 mg tirzepatide SC) throughout. The TFLs will also be presented by BMI group (Low BMI, High BMI, and Overall). The following is a list of the injection sites that will be used in the TFLs.

Injection site	Order in TFL
Abdomen	1
Upper Arm	2
Thigh	3

## 7. SAMPLE SIZE JUSTIFICATION

Approximately 54 subjects will be enrolled to ensure that at least 36 evaluable subjects complete the study, with at least 12 subjects completing per treatment sequence. With 36 subjects, we expect the two one-sided t-tests (TOST) for equivalence applied to the log-normal mean ratio to have a power of at least 98% for each of the 4 tests on the primary objective. This assumes a nominal expected mean ratio of 1.05, a coefficient variation of 19.6%, and significance level of 0.05 of each one-sided test when testing against an upper limit of 1.25 and lower limit of 0.80. The source of the choice of coefficient of variation is from the final results of study I8F-MC-GPGE. For balance and the evaluation of the secondary objective of effect of BMI, the 54 subjects will be enrolled according to their BMI category such that each category enrolls approximately 27 subjects and retains 6 completers per treatment sequence.

## **8. DEFINITION OF ANALYSIS POPULATIONS**

The “Safety” population will consist of all subjects who received at least 1 dose of tirzepatide, whether or not they completed all protocol requirements.

The “Pharmacokinetic” population will consist of all subjects who received at least 1 dose of tirzepatide and have evaluable PK data.

All protocol deviations that occur during the study will be considered for their severity/impact and will be taken into consideration when subjects are assigned to analysis populations.

## **9. STATISTICAL METHODOLOGY**

### **9.1 General**

Data listings will be provided for all data that is databased. Summary statistics and statistical analysis will only be presented for data where detailed in this SAP. For continuous data, summary statistics will include the arithmetic mean, arithmetic standard deviation (SD), median, min, max and N; for log-normal data (e.g. the PK parameters: area under the concentration versus time curve [AUC] and maximum observed drug concentration [ $C_{max}$ ]) the geometric mean and geometric coefficient of variation (CV%) will also be presented. For categorical data, frequency count and percentages will be presented. Data listings will be provided for all subjects up to the point of withdrawal, with any subjects excluded from the relevant population highlighted. Summary statistics and statistical analyses will generally only be performed for subjects included in the relevant analysis population. For the calculation of summary statistics and statistical analysis, unrounded data will be used.

Mean change from baseline is the mean of all individual subjects' change from baseline values. Each individual change from baseline will be calculated by subtracting the individual subject's baseline value from the value at the timepoint. The individual subject's change from baseline values will be used to calculate the mean change from baseline using a SAS procedure such as Proc Univariate.

Where specified in the sections below, safety data will be summarised by BMI group (Low, High and Overall) and also by injection site location (Abdomen, Upper Arm and Thigh), but not by injection site within BMI group. For the secondary objective, the PK data will be presented by injection site within BMI group.

Data analysis will be performed using SAS® Version 9.4 or greater.

### **9.2 Demographics and Subject Disposition**

Subject disposition will be listed. The demographic variables age, sex, race, ethnicity, body weight, height and BMI will be summarized by BMI group and listed. All other demographic variables will be listed only.

### 9.3 Pharmacokinetic Assessment

#### 9.3.1 Pharmacokinetic Analysis

Pharmacokinetic parameter estimates will be determined using non-compartmental procedures in validated software program (Phoenix WinNonlin Version 8.1 or later).

Plasma concentrations of tirzepatide (LY3298176) will be used to determine the following PK parameters, when possible:

Parameter	Units	Definition
AUC(0-t last )	ng.h/mL	Area under the concentration versus time curve from time zero to time t, where t is the last time point with a measurable concentration
AUC(0-∞)	ng.h/mL	Area under the concentration versus time curve from time zero to infinity
%AUC(t last -∞)	%	Percentage of AUC(0-∞) extrapolated
C max	ng/mL	Maximum observed drug concentration
t max	h	Time of maximum observed drug concentration
t ½	h	Half-life associated with the terminal rate constant ( $\lambda_z$ ) in non-compartmental analysis
CL/F	L/h	Apparent total body clearance of drug calculated after extra-vascular administration
V Z/F	L	Apparent volume of distribution during the terminal phase after extra-vascular administration
V SS/F	L	Apparent volume of distribution at steady state after extra-vascular administration

Additional PK parameters may be calculated, as appropriate. The PK parameters will be summarized by injection site and BMI group (Low BMI, High BMI, and Overall).

The software and version used for the final analyses will be specified in the clinical study report. Any exceptions or special handling of data will be clearly documented within the final study report.

Formatting of tables, figures and abbreviations will follow the Eli Lilly Global PK/PD/TS Tool: NON-COMPARTMENTAL PHARMACOKINETIC STYLE GUIDE. The version of the tool effective at the time of PK analysis will be followed.

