## 7. Treatment

### 7.1. Treatment Administered

This study involves a comparison of tirzepatide administered as single 5-mg SC injections delivered via an autoinjector to the upper arm and thigh in comparison to the abdomen.

[Table GPHI.2](#) shows the treatment regimens.

When administered in the abdomen, the injection will be administered to the lower abdominal quadrant, approximately 5 cm from the umbilicus. Detailed instructions for use of the autoinjector will be provided by the sponsor. Only a limited number of clinical site staff will perform the SC administration for consistency reasons.

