#### **10.3.2. Pharmacokinetic Analyses**

##### **10.3.2.1. Pharmacokinetic Parameter Estimation**

Pharmacokinetic parameter estimates for tirzepatide will be calculated by standard noncompartmental methods of analysis.

The primary PK parameters for analysis will be  $C_{max}$  and area under the concentration versus time curve from zero to infinity ( $AUC[0-\infty]$ ). Other noncompartmental parameters, such as time to  $C_{max}$  ( $t_{max}$ ), area under the concentration versus time curve from zero to the last measurable concentration ( $AUC[0-t_{last}]$ ), half-life associated with the terminal rate constant in noncompartmental analysis ( $t_{1/2}$ ), apparent clearance (CL/F), and apparent volume of distribution (V/F) may be reported.

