### **11. CHANGES FROM THE PROTOCOL SPECIFIED STATISTICAL ANALYSES**

There were no changes from the protocol specified statistical analyses.

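### The SAP's Vss/F, from single subcutaneous doses with no intravenous reference, would carry absorption time under a disposition label if computed as CL/F × MRT

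*SAP*

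**What the plan says.** SAP 9.3.1 sets the method: "Pharmacokinetic parameter estimates will be determined using non-compartmental procedures in validated software program". Plasma concentrations "will be used to determine the following PK parameters, when possible", and the table that follows lists two volumes, Vz/F (terminal phase) and Vss/F, the latter defined as "Apparent volume of distribution at steady state after extra-vascular administration". On presentation it says: "The PK parameters will be summarized by injection site and BMI group". SAP 9.1 adds that, for the secondary objective, PK data are shown by site within BMI group.

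The General and Individual PK Parameter Rules in SAP 9.3.1 cover sampling times, Cmax, tmax, AUC, half-life and values below quantitation. They give no formula for Vss/F or MRT and do not mention absorption time.

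Protocol 7.1 describes the treatments as "single 5-mg SC injections delivered via an autoinjector to the upper arm and thigh in comparison to the abdomen". Table GPHI.2 confirms the SC route for all three sites. No treatment is intravenous.

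Protocol 10.3.2.1 names one volume among its optional parameters: "apparent volume of distribution (V/F) may be reported".

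**The concern.** Non-compartmental Vss is clearance times the mean residence time of drug once it is in the body. After an SC dose, the MRT read from the profile also contains the mean time spent being absorbed. Separating the two parts needs an intravenous profile, and this study has none. A value computed as CL/F × MRT from the SC profile can be obtained for almost any complete profile, so the qualifier on the parameter list does not screen it out. It is nevertheless not the volume that its label names.

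This matters more here than in most single-dose studies because injection site is the treatment factor. Protocol 3.1 gives a possible difference in absorption profile as part of the rationale. The term that contaminates Vss/F is therefore one that may differ between the columns of the planned table. A reader of the study report could take a difference in absorption rate for a difference in distribution between sites or BMI groups.

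**Working it through.** **The plan's own figure.** The documents give no number for Vss/F. The only related design figure is the power of at least 98% with 36 completers (protocol 10.1, SAP 7). With s_w = √ln(1 + 0.196²) = 0.194, SE = 0.194 × √(2/36) = 0.0458, a true ratio of 1.05 and limits of 0.80 to 1.25, the power is 98.2% on 34 degrees of freedom and 98.3% on 68. The stated figure reproduces, and it does not involve Vss/F.

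**Direction of the bias (no compartmental model needed).** Write MRT_d for the disposition MRT and MAT for mean absorption time.

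1. After SC dosing, AUMC/AUC = MRT_sc = MRT_d + MAT.
2. The target is Vss/F = (CL/F) × MRT_d.
3. The computed value is (CL/F) × MRT_sc = Vss/F + (CL/F) × MAT.
4. Computed over true = 1 + MAT/MRT_d, which always exceeds 1.

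**Size of the bias (model assumed).** Protocol 3.2 gives a terminal half-life of about 5 days (120 h) and a tmax of 24 to 72 h. Assume one compartment, first-order absorption, and a terminal half-life that reflects elimination.

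- ke = ln 2/120 = 0.00578 per h, so MRT_d = 1/ke = 173.1 h.
- ka solves tmax = ln(ka/ke)/(ka − ke).
- MAT = 1/ka, and the overstatement is MAT/MRT_d.

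| tmax (h) | ka (per h) | MAT (h) | MAT/173.1 |
|---|---|---|---|
| 24 | 0.138 | 7.2 | 4.2% |
| 36 | 0.0781 | 12.8 | 7.4% |
| 48 | 0.0513 | 19.5 | 11.3% |
| 72 | 0.0274 | 36.5 | 21.1% |

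**Spurious ratio between two sites with the same true volume and the same F.**

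- 24 versus 36 h: 1.074/1.042 = 1.03
- 36 versus 48 h: 1.113/1.074 = 1.04
- 24 versus 48 h: 1.113/1.042 = 1.07
- 24 versus 72 h: 1.211/1.042 = 1.16 (an extreme)

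**Check on the planned schedule.** Noise-free profiles from the same model were analysed with the SAP's linear-log trapezoidal rule at the protocol's sampling times, taking Day 36 as 840 h. CL/F × MRT exceeded the true volume by 5.2%, 12.0% and 22.0% at tmax 24, 48 and 72 h. This is the identity's result plus about one percentage point of trapezoidal error. Vz/F from the same profiles was within 0.6% of truth, so in this model the absorption-time bias affects Vss/F and not the other volume in the table.

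**The case against.** Four points can be made for the plan as written.

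- **No formula is stated.** The inflation follows only if Vss/F is computed as CL/F × MRT from the SC profile. This stands as a condition on the finding. It is, however, the usual non-compartmental route, and nothing in SAP 9.3.1 points to another.
- **Nothing decisive depends on Vss/F.** It is not an endpoint in Table GPHI.1. The model-based comparisons in SAP 9.3.2 cover AUC(0-∞), Cmax and AUC(0-tlast), and tmax is compared non-parametrically. A reader would therefore see an absorption-rate difference beside the Vss/F row. This stands and limits the consequence.
- **The other apparent parameters are not pure disposition values either.** CL/F and Vz/F both divide by F, and relative F between sites is what the study measures. This also stands: deleting Vss/F does not make volume comparisons between sites free of bioavailability. Vss/F carries the same dependence on F and adds absorption time to it.
- **A footnote would be enough.** A stated formula with a warning against comparing sites would prevent the misreading. It would leave in the table a number that does not estimate its named quantity, while Vz/F is already there.

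Two stronger readings are tempting, and the documents do not support them. First, a reader might infer an undeclared change, since the protocol names only V/F while SAP 11 states: "There were no changes from the protocol specified statistical analyses". But the list in protocol 10.3.2.1 is introduced as examples and is optional, so an added descriptive parameter contradicts neither document. Second, a reader might take 24 and 72 h as typical values of two sites and expect a spurious difference of 16%. Protocol 3.1 says that the earlier Phase 1 and 2 trials injected into the abdomen. The range therefore describes spread at one site, not a contrast between sites.

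**Conclusion.** The point holds as a limited technical error. A non-compartmental Vss/F is planned from SC data alone, with no means of removing absorption time. Computed as CL/F × MRT, it overstates the apparent steady-state volume by CL/F × MAT. The upward direction follows from that calculation and not from the compartmental model.

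The size does rest on assumptions: one compartment, first-order absorption, and the protocol's approximate half-life and tmax range. On those, the overstatement is about 4% to 21%. Moderate differences in tmax between sites (24 versus 36 h, or 24 versus 48 h) give a false difference of about 3% or 7%. The documents give no tmax for the upper arm or thigh, so the actual between-site difference is unknown.

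The effect is confined to one descriptive parameter. It does not touch the primary or secondary AUC(0-∞) and Cmax comparisons, the equivalence criterion or the power.

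**What to change.** Delete the Vss/F row from the parameter table in SAP 9.3.1, its entry in SAP section 2, and any matching line in the TFL shells. Keep Vz/F as the reported volume; nothing that the protocol names is lost.

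If a residence measure is wanted, report MRT after SC dosing under that name and state that it includes absorption time. If Vss/F is kept regardless, the least that is needed is a stated formula and a table footnote saying that the value includes absorption time and should not be compared between sites or BMI groups.

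The cost is one row in the SAP and its tables. Sampling, data collection, sample size and subjects are unaffected.

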#### General PK Parameter Rules

- Actual sampling times will be used in the final analyses of individual PK parameters, except for non-bolus pre-dose sampling times which will be set to zero.
- Cmax and tmax will be reported from observed values. If Cmax occurs at more than one timepoint, tmax will be assigned to the first occurrence of Cmax.

- AUC parameters will be calculated using a combination of the linear and logarithmic trapezoidal methods (linear-log trapezoidal rule). The linear trapezoidal method will be applied up to  $t_{max}$  and then the logarithmic trapezoidal method will be used after  $t_{max}$ . The minimum requirement for the calculation of AUC will be the inclusion of at least three consecutive concentrations above the lower limit of quantitation (LLOQ), with at least one of these concentrations following  $C_{max}$ .
- AUC(0-∞) values where the percentage of the total area extrapolated is more than 20% will be flagged. Any AUC(0-∞) value excluded from summary statistics will be noted in the footnote of the summary table.
- Half-life ( $t_{1/2}$ ) will be calculated, when appropriate, based on the apparent terminal log-linear portion of the concentration-time curve. The start of the terminal elimination phase for each subject will be defined by visual inspection and generally will be the first point at which there is no systematic deviation from the log-linear decline in plasma concentrations. Half-life will only be calculated when a reliable estimate for this parameter can be obtained comprising of at least 3 data points. If  $t_{1/2}$  is estimated over a time window of less than 2 half-lives, the values will be flagged in the data listings. Any  $t_{1/2}$  value excluded from summary statistics will be documented in the footnote of the summary table.
- A uniform weighting scheme will be used in the regression analysis of the terminal log-linear portion of the concentration-time curve.
- The parameters based on the last observed quantifiable drug concentration ( $C_{last}$ ) will be reported.

### Individual PK Parameter Rules

- Only quantifiable concentrations will be used to calculate PK parameters with the exception of special handling of certain concentrations reported below the lower limit of quantitation (BQL). Plasma concentrations reported as BQL will be set to a value of zero when all of the following conditions are met:
  - The compound is non-endogenous.
  - The samples are from the initial dose period for a subject or from a subsequent dose period following a suitable wash-out period.
  - The time points occur before the first quantifiable concentration.
- All other BQL concentrations that do not meet the above criteria will be set to missing.
- Also, where two or more consecutive concentrations are BQL towards the end of a profile, the profile will be deemed to have terminated and therefore any further quantifiable concentrations will be set to missing for the calculation of the PK parameters unless it is considered to be a true characteristic of the profile of the drug.

### **Individual Concentration vs. Time Profiles**

- Individual concentrations will be plotted utilizing actual sampling times.
- The terminal point selections will be indicated on a semi-logarithmic plot.

### **Average Concentration vs. Time Profiles**

- The average concentration profiles will be graphed using scheduled (nominal) sampling times.
- The average concentration profiles will be graphed using arithmetic average concentrations.
- The pre-dose average concentration for single-dose data from non-endogenous compounds will be set to zero. Otherwise, only quantifiable concentrations will be used to calculate average concentrations.
- Concentrations at a sampling time exceeding the sampling time window specified in the protocol, or  $\pm 10\%$ , will be excluded from the average concentration profiles.
- Concentrations excluded from the mean calculation will be documented in the final study report.
- A concentration average will be plotted for a given sampling time only if 2/3 of the individual data at the time point have quantifiable measurements that are within the sampling time window specified in the protocol or  $\pm 10\%$ . An average concentration estimated with less than 2/3 but more than 3 data points may be displayed on the mean concentration plot if determined to be appropriate and will be documented within the final study report.

### **Treatment of Outliers during Pharmacokinetic Analysis**

Application of this procedure to all PK analyses is not a requirement. Rather, this procedure provides justification for exclusion of data when scientifically appropriate. This procedure describes the methodology for identifying an individual value as an outlier for potential exclusion, but does not require that the value be excluded from analysis. The following methodology will not be used to exclude complete profiles from analysis.

#### Data within an Individual Profile

A value within an individual profile may be excluded from analysis if any of the following criteria are met:

- For PK profiles during single dosing of non-endogenous compounds, the concentration in a pre-dose sample is quantifiable.

- For any questionable datum that does not satisfy the above criteria, the profile will be evaluated and results reported with and without the suspected datum.

#### Data between Individual Profiles

1. If  $n < 6$ , then the dataset is too small to conduct a reliable range test. Data will be analyzed with and without the atypical value, and both sets of results will be reported.
2. If  $n \geq 6$ , then an objective outlier test will be used to compare the atypical value to other values included in that calculation:
  - a. Transform all values in the calculation to the logarithmic domain.
  - b. Find the most extreme value from the arithmetic mean of the log transformed values and exclude that value from the dataset.
  - c. Calculate the lower and upper bounds of the range defined by the arithmetic mean  $\pm 3*SD$  of the remaining log-transformed values.
  - d. If the extreme value is within the range of arithmetic mean  $\pm 3*SD$ , then it is not an outlier and will be retained in the dataset.
  - e. If the extreme value is outside the range of arithmetic mean  $\pm 3*SD$ , then it is an outlier and will be excluded from analysis.

If the remaining dataset contains another atypical datum suspected to be an outlier and  $n \geq 6$  following the exclusion, then repeat step 2 above. This evaluation may be repeated as many times as necessary, excluding only one suspected outlier in each iteration, until all data remaining in the dataset fall within the range of arithmetic mean  $\pm 3*SD$  of the log-transformed values.

